#### Ethical consideration

An Ethical Approval of Scientific Research were obtained from the Research Ethics Committee at the University of Hail (Ethical Approval No: H-2025-560), in strict adherence to the principles outlined in the Declaration of Helsinki. This ethical clearance ensured that the study design and implementation met the highest standards of human subject research ethics. Furthermore, official permissions will be secured from the responsible authorities of the respective study settings, following a clear and thorough explanation of the study's objectives and methods to these authorities. This careful attention to ethical and administrative approvals underscores the researchers' commitment to conducting the study responsibly and in accordance with established ethical guidelines.

#### Expected Outcomes

The expected outcomes of this study will include a significant reduction in BMI, FBG, RBS, and HbA1c among participants who receive Fenugreek seed powder in addition to standard diabetes care. It is anticipated that participants in the intervention group will experience better glycemic control and more favorable weight management outcomes compared to those receiving standard care alone.

Furthermore, this study is expected to provide evidence supporting the use of Fenugreek as a culturally acceptable, affordable, and safe dietary supplement that complements conventional treatment for adults with T2DM and obesity in Saudi Arabia. The findings may contribute to local public health strategies aimed at non-pharmacological interventions for chronic metabolic diseases.

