T2DM is commonly associated with a cluster of conditions including high blood sugar, insulin resistance, dyslipidemia, hypertension, and obesity, which often occur together. The development of T2DM is influenced by a combination of genetic, environmental, and behavioral factors. As such, addressing this complex condition requires integrated strategies to manage the interconnected health issues it involves [11–13].

In recent years, conventional medical therapies for obesity have shown limited effectiveness. Evidence suggests that obese patients increasingly turn to alternative remedies in an effort to lose weight. These remedies include nutritional medicinal plants such as Fenugreek, which is one of

the oldest and most widely used herbs due to its safety, affordability, availability, and ease of use [3, 14–18].

Fenugreek has demonstrated medicinal and nutritional benefits. It has been used to reduce body weight and manage metabolic complications, as it contains essential active ingredients (e.g., flavonoids, fiber, alkaloids, and amino acids) that reduce intestinal absorption of carbohydrates and improve glucose regulation in the liver and muscle tissue. It also possesses antidiabetic, antibacterial, anticancer, antioxidant, and anti-anorexic properties [16, 19–21].

Additionally, Fenugreek may act as an appetite suppressant by increasing the levels of cholecystokinin and glucagon-like peptide-1 hormones, which are involved in regulating appetite. When added to carbohydrate-containing meals, its high fiber content enhances the sensation of fullness among overweight or obese individuals, leading to reduced food intake and weight loss [21, 22].

Fenugreek may also increase insulin sensitivity by enhancing the insulin signaling pathway through upregulation of insulin receptors, thereby promoting glucose uptake and reducing postprandial blood glucose levels. Its amino acid content (notably 4-hydroxyisoleucine) stimulates insulin release and helps regulate blood sugar, ultimately reducing food cravings and promoting weight loss. Therefore, Fenugreek has proven beneficial for patients with diabetes or insulin resistance, as it reduces the blood sugar response to carbohydrate meals [23–25].

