In Saudi Arabia, where obesity and T2DM are prevalent due to lifestyle factors, Fenugreek offers a culturally suitable and cost-effective dietary intervention. Investigating its effects on obesity and glycemic control could support its inclusion in national health strategies and the development of comprehensive treatment plans that integrate both medical and non-medical approaches [31, 32].

This study aims to address the existing research gap by generating region-specific evidence on the effectiveness of Fenugreek supplementation. The findings will support evidence-based practice and inform public health policies tailored to the Saudi population. Ultimately, the study seeks to improve health outcomes, ensure patient safety, and reduce morbidity and mortality among adults with diabetes and obesity.

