#### Data collection

Data will be collected from each participant through an individually administered interview schedule. The structured interview tool, developed by the researchers, will be designed to gather both personal and clinical data relevant to the study. Personal data will include participants' age (in years), gender, and Body Mass Index (BMI), which will be calculated using the following equation:

$$\text{BMI} = \text{weight (kg)} / \text{height}^2 (\text{m}^2).$$

Weight will be measured in kilograms (kg) using a calibrated scale, with participants wearing minimal clothing and no shoes. Height will be measured in meters (m) using a stadiometer, with participants standing upright on a flat surface (neither slumping nor stretching), barefoot, and with their heels, shoulders, and the back of the head aligned vertically, looking straight ahead without tilting the head up or down [33, 34].

Clinical data will include:

Fasting Blood Sugar (FBS) in mg/dL,

Random Blood Sugar (RBS) in mg/dL, and

Glycated Hemoglobin (HbA1c) in percentage (%).

BMI, FBS, and RBS will be measured at four time points: baseline, and at one, two, and three months. HbA1c will be assessed at two time points: baseline and at three months.

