#### Intervention Procedures

Participants will be equally divided into two groups: a study group and a control group, each comprising 40 individuals. Following the provision of informed consent, participants will be randomly assigned to either the study group—which will receive Fenugreek supplementation in addition to standard care—or the control group, which will receive standard care alone. Randomization will be performed using a computer-generated random number list to ensure unbiased allocation.

Due to the practical challenges associated with dietary interventions and the absence of placebo controls in this setting, blinding will not be feasible for participants or the researchers administering the intervention. Consequently, participants will be aware of their group assignments. Nonetheless, outcome assessors and data analysts will remain blinded to group allocation throughout the data collection and analysis phases to minimize detection and performance biases.

Participants in the study group will continue their prescribed anti-diabetic treatment and adhere to a standardized dietary plan, in addition to consuming Fenugreek seed powder (10 g in sachet form) daily before breakfast and dinner for a duration of three months. In contrast, the control group will receive only their prescribed anti-diabetic treatment while following the same dietary plan. To enhance adherence to the intervention, researchers will maintain weekly telephone contact with participants in the study group, emphasizing the importance of compliance with both the Fenugreek supplementation and dietary plan.

Upon completion of the three-month intervention, a comparative analysis will be conducted between the study and control groups to evaluate the impact of Fenugreek supplementation on obesity and hyperglycemia in adults with T2DM.

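### The protocol expects this study to supply evidence that fenugreek is safe, but no listed data item or analysis concerns adverse events or symptoms

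*Protocol*

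**What the plan says.** The Protocol's Expected Outcomes section first names reductions in BMI, fasting and random glucose and HbA1c. It then adds that "this study is expected to provide evidence supporting the use of Fenugreek as a culturally acceptable, affordable, and safe dietary supplement".

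The Data collection section describes an interview tool that "will be designed to gather both personal and clinical data relevant to the study". The personal items listed are age, gender and BMI; the clinical items are FBS, RBS and HbA1c. The schedule is: "BMI, FBS, and RBS will be measured at four time points: baseline, and at one, two, and three months"; and "HbA1c will be assessed at two time points: baseline and at three months".

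The only other participant contact described is under Intervention Procedures: "researchers will maintain weekly telephone contact with participants in the study group, emphasizing the importance of compliance". The same section says that participants know their group, while "outcome assessors and data analysts will remain blinded to group allocation throughout the data collection and analysis phases".

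Safety appears in two other places, both in the introduction. One gives it as a reason why fenugreek is widely used: "due to its safety, affordability, availability, and ease of use". The other is a closing statement of purpose: "the study seeks to improve health outcomes, ensure patient safety, and reduce morbidity and mortality among adults with diabetes and obesity". The aim and the two hypotheses concern BMI and blood glucose only.

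**The concern.** A conclusion that a study is expected to reach should have a data source in that study. Here the efficacy expectations have one and the safety expectation does not. A report written to match the Expected Outcomes section could call the supplement safe on the strength of a trial that, as described, did not ask about harm.

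This matters because the same section looks ahead to use of the findings in local public health strategies, and the introduction looks ahead to national ones. The gap is also not one that a statistical analysis plan can close. Such a plan can say how harms are tabulated, but it cannot analyse data that were not collected.

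Two neighbouring words in the sentence, on cultural acceptability and affordability, are in the same position: no listed item measures either.

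**Working it through.** The plan gives no figure on harms, so there is none to reproduce. Its sample-size calculation (78, raised to 80) is a precision calculation for a proportion and plays no part here.

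**Step 1: set the expected conclusions against the listed data.**

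| Expected in Expected Outcomes | Listed under Data collection | Named under Statistical analysis |
|---|---|---|
| Lower BMI | BMI, 4 time points | t-test, repeated-measures ANOVA |
| Lower fasting and random glucose | FBS and RBS, 4 time points | t-test, repeated-measures ANOVA |
| Lower HbA1c | HbA1c, 2 time points | t-test |
| Safe | no adverse-event or symptom item | no harm analysis |
| Culturally acceptable | no item | none |
| Affordable | no item | none |

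The test names in the first three rows are those that the section gives for quantitative variables; it does not assign them outcome by outcome.

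**Step 2: could another contact supply the data?** The weekly calls go to one arm and their stated purpose is adherence. Even if harms were noted on them, there would be no matching record in the control group.

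**Step 3: could the glucose readings serve?** FBS and RBS are listed as outcome measures. They would show a low value only if it were present at a scheduled reading, and they say nothing about any other kind of harm.

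**Step 4: what could be said if harms were recorded?** Input: 40 participants in the study group (Intervention Procedures). With zero events among n, the exact upper limit solves (1 − p)^n = α.

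- One-sided 95%: 1 − 0.05^(1/40) = 0.0722, or 7.2%.
- Two-sided 95%: 1 − 0.025^(1/40) = 0.0881, or 8.8%.

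The plan states no expected dropout. Assuming 10% or 20% loss for illustration:

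| Exposed and followed | One-sided upper limit | Two-sided upper limit |
|---|---|---|
| 40 | 7.2% | 8.8% |
| 36 | 8.0% | 9.7% |
| 32 | 8.9% | 10.9% |

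The chance of seeing at least one case among 40 is 1 − (1 − p)^40. For a true rate of 1% this is 33%, for 2% it is 55%, and for 5% it is 87%.

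These figures describe what an added harm record could show. They do not measure an error in the document.

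**The case against.** The strongest reply is that the sentence promises no safety finding. The introduction already describes fenugreek as safe and affordable, so the adjectives may be carried over from the literature, with the study supplying only evidence on efficacy. On that reading no safety conclusion from trial data is forecast. This stands as a possible reading, and it would reduce the matter to wording. It is not the natural one, because the sentence sits under Expected Outcomes and names this study as the source of the evidence. A reader cannot tell which was meant, so the sentence needs correcting on either reading.

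It can also be said that Expected Outcomes is closing prose and not an instruction, and that the introduction's reference to patient safety is a long-term aspiration. The second part is right. The same introductory sentence mentions mortality, and nobody would fault the study for having no mortality endpoint, so that sentence is weak support and the point does not rest on it.

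A reader might infer that no adverse event would be recorded anywhere, or that harms among the 40 exposed participants would go undescribed. The documents do not support that. The data lists are introduced as what will be included and need not be exhaustive, some pages were removed before review, and describing the calls by their purpose does not say that nothing else is noted.

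**Conclusion.** The point holds in a limited form. In the text available for review, the word safe in Expected Outcomes has no listed data item and no named analysis behind it. Read naturally, the sentence attributes safety evidence to the study, and the listed data would not support it. If only background was meant, the text should say so.

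The size is confined to that conclusion. A reader might infer that the efficacy results are weakened too; they are not, since the BMI and glucose comparisons do not depend on this sentence. Nor is the study at fault for having no safety hypothesis, because an efficacy study may leave safety aside provided that it does not then forecast a safety conclusion.

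The verdict assumes that the removed pages contain no harm record. If one is provided for there, the Data collection section should refer to it, and the precision limit of about 40 exposed participants still applies. The correction is worth making because it is cheap and changes what the study can claim.

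**What to change.** Choose one of two.

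**(a) Record harms.** Add to Data collection a short fixed set of adverse-event and symptom questions, asked in the same words in both arms at the visits already scheduled, and only after that visit's outcome measurements have been recorded. Report counts by arm with exact 95% confidence intervals. Limit the statement in Expected Outcomes to what about 40 exposed participants can show, quoting the limits for 0 of 40 (7.2% one-sided, 8.8% two-sided). The cost is slightly longer visits and one descriptive table. There is some risk of unblinding the assessors, which the ordering reduces but does not remove. Participants know their group, so self-reports are open to expectation and the comparison by arm is descriptive only.

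**(b) Drop the claim.** Delete the word safe from Expected Outcomes, or attribute it to the cited background. The cost is a small edit; the study then says nothing on safety.

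In either case, mark cultural acceptability and affordability as background or as not assessed.
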